5.1.3.2 Concomitant medication start date imputation

Rules for imputing the CM start date:

The following table explains the notation used in the logic matrix. Please note that missing start dates will not be imputed.

	Day	Month	Year
Partial CMD Start Date	Not used	MON	YYYY
Treatment Start Date	Not used	TRTM	TRTY

The following matrix explains the logic behind the imputation.

	MON MISSING	MON < TRTM	MON = TRTM	MON > TRTM
YYYY MISSING	(1) Uncertain	(1) Uncertain	(1) Uncertain	(1) Uncertain
YYYY < TRTY	(2.a) Before Treatment Start	(2.b) Before Treatment Start	(2.b) Before Treatment Start	(2.b) Before Treatment Start
YYYY = TRTY	(4.a) Uncertain	(4.b) Before Treatment Start	(4.a) Uncertain	(4.c) After Treatment Start
YYYY > TRTY	(3.a) After Treatment Start	(3.b) After Treatment Start	(3.b) After Treatment Start	(3.b) After Treatment Start

1. If the CM start date year value is missing, the imputed CM start date is set to one day prior to treatment start date.
2. If the CM start date year value is less than the treatment start date year value, the CM started before treatment. Therefore:
 - a. If the CM month is missing, the imputed CM start date is set to the mid-year point (01JulYYYY).
 - b. Else if the CM month is not missing, the imputed CM start date is set to the mid-month point (15MONYYYY).
3. If the CM start date year value is greater than the treatment start date year value, the CM started after treatment. Therefore:
 - a. If the CM month is missing, the imputed CM start date is set to the year start point (01JanYYYY).
 - b. Else if the CM month is not missing, the imputed CM start date is set to the month start point (01MONYYYY).
4. If the CM start date year value is equal to the treatment start date year value:
 - a. And the CM month is missing or the CM month is equal to the treatment start date month, then the imputed CM start date is set to one day prior treatment start date.
 - b. Else if the CM month is less than the treatment start date month, the imputed CM start date is set to the mid-month point (15MONYYYY).

- c. Else if the CM month is greater than the treatment start date month, the imputed CM start date is set to the month start point (01MONYYYY).

If complete imputed CM end date is available and the imputed CM start date is greater than the (imputed) CM end date, then imputed CM start date should be set to the (imputed) CM end date.

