5.5.8 Prohibited medication

Use of the treatments displayed in the below table is NOT allowed* according to the table below. Each concomitant drug must be individually assessed against all exclusion criteria and the tables below to see if it is allowed. If in doubt, the investigator should contact the Novartis medical monitor or designee before randomizing a patient or allowing a new medication to be started. This table is not considered all-inclusive. Medications should be assessed for adherence to the indication and other inclusion/exclusion criteria. These medications are also prohibited if administered for other indications.

Table 5-4 Prohibited medication

Medication	Prohibition period (Minimum cessation prior to start of run-in Visits)
Other investigational drugs	30 days or 5 half-lives, whichever is longer
Live attenuated vaccine	30 days
Other CR Th2 antagonists (e.g., ramatroban)	7 days or 5 half-lives whichever is longer
Short-acting anticholinergics	8 hours
Fixed combinations of short-acting β_2 -agonists and short-acting anticholinergics	8 hours
Systemic mast cell stabilizers (e.g., cromoglycate, nedocromil, ketotifen)	7 days
Monoclonal antibodies, investigational or approved, for the treatment of asthma (e.g., omalizumab)*	6 months

Medication	Prohibition period (Minimum cessation prior to start of run-in Visits)
Simvastatin > 20 mg, atorvastatin > 40 mg, pravastatin > 40 mg, or pitavastatin > 2 mg total daily dose	7 days
Rifampin, probenecid, ritonavir and valproic acid (i.e. medications blocking several pathways important for the elimination of QAW039 (broadrange UGT inhibition and/or inhibition of OAT3, OATP1B3, MXR and P-gp)).	7 days
Methotrexate, gold salts, cyclosporine, troleandomycin, azathioprine, other immunomodulator drugs	6 months
Systemic (oral, intravenous, intramuscular) corticosteroids for non-asthma conditions	3 months
LTRAs	New onsets (during study duration)
*Biologics are allowed directly after randomization as part of the flexible therapy.	

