6.4.5 Biologic therapy administered during the treatment period

As part of the flexible therapy, investigators are allowed to prescribe biologics from randomization visit onwards.

Given the delay to get access to the treatment in some countries, the date of prescription by the investigator should be recorded in addition to the start date and end date of the treatment. The dose, unit and reason for the treatment will also be collected.

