The total systemic corticosteroid dose in mg prednisone/prednisolone (or equivalent) over 52 weeks of treatment will be analyzed using the Wilcoxon-Mann-Whitney rank sum test (Van Elteren test). For overall population analysis will be stratified by randomization stratum – blood eosinophils levels (≥ 250 cells/ μl and < 250 cells/ μl). For subgroup with blood eosinophils ≥ 250 cells/ μl , analysis will not include stratification factor. The summary statistics for total SCS dose by treatment group will be provided.

The primary estimand will quantify the treatment effect based on on-treatment data. The total SCS dose data will be aggregated into monthly data for analysis. The primary estimand will account for different post-randomization events as follows:

- Use of rescue medications: Efficacy data collected during use of rescue medication will be used for analysis.

- Early discontinuation of study drug (prior to completing 52 weeks of treatment period): For the patients discontinuing study drug early, the total SCS dose for 52 weeks will be obtained as annualized SCS dose. For example if patient took 280 mg for 7 months then for 12 months patient will be taking $280 \times 12/7 = 480$ mg total SCS dose.
- Use of biologics prior to discontinuation of treatment: Efficacy data collected during the use of biologics will be set to missing, since use of biologics can confound efficacy data. Biologics are usually taken for long period of time. Thus, after replacing SCS dose with missing, patient will not have data available for remaining duration of the study. The total SCS dose will be obtained as annualized dose as explained above.

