2.7.1.5 Proportion of patients with prescription of biologic treatment

The proportion of patients with any prescription of biologic therapy during the on-treatment period will be presented. Events which occur during on-treatment period will be included.

2.7.1.6 Summary of change from baseline of daytime and nighttime symptom scores by 4-week intervals during on-treatment period

The daytime and night time symptom scores will be collected using validated electronic patient diary. Scoring of measures: A range of response categories for each question from 0 to 6 (0 – totally controlled, 6 – extremely poorly controlled) is used in the daytime asthma symptom scale. Response categories ranging from 0 (indicating no awakening with asthma symptoms) to 3 (indicating awake all night) are used in the nocturnal diary scale. Daily daytime symptom scores will be computed as the average of the available scores on four questions on the daytime symptom scale.

The mean daytime asthma symptom scores/nighttime symptom score will be calculated for each patient for each 4 week visit interval and over on-treatment period. The average score for each time interval is defined as the sum of daily scores (based on all the available questions) divided by the number of days where diary records have been made on nighttime/daytime score for that visit interval. The non-missing data within each 4 week interval in treatment period will be used to calculate the mean value, as long as there are at least 14 days with non-missing e-diary data (based on all the available questions) in a 4-week period. Otherwise, the value will be set as missing.

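### SAP 5.1.3.2 rule 4a (and rule 1, if it applies) can date a biologic to the day before first dose, a date the protocol rules out, and so can blank a patient's whole on-treatment SCS record

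*SAP*

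**What the plan says.** SAP 5.1.3.2 gives one set of rules for incomplete start dates of all concomitant medication. Rule 4a applies when the start year is the treatment-start year and the month is either missing or "is equal to the treatment start date month, then the imputed CM start date is set to one day prior treatment start date". Rule 1 reads: "If the CM start date year value is missing, the imputed CM start date is set to one day prior to treatment start date". The lead-in to the same section says: "Please note that missing start dates will not be imputed". Rules 3a, 3b and 4c place the other post-randomization partial dates at the start of the known later year or month. No medication class is treated separately.

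For the primary endpoint, SAP 2.5.2 states: "Efficacy data collected during the use of biologics will be set to missing, since use of biologics can confound efficacy data". It expects biologic use to last for the rest of the study and annualises what was observed beforehand. SAP 5.1.3.1 does not impute end dates for ongoing records.

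The protocol bars biologics for six months before run-in (exclusion 3). The footnote to Table 5-4 in 5.5.8 says: "Biologics are allowed directly after randomization as part of the flexible therapy". Protocol 6.4.5 allows prescription from the randomization visit, which Table 6-1 places at Day 1, and requires that "the date of prescription by the investigator should be recorded in addition to the start date and end date of the treatment". Protocol 5.5.5 sends step-up changes, with biologics among its examples, to the Prior and Concomitant Medications CRF.

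**The concern.** Day -1 is a cautious default when the only question is whether a medication was prior or concomitant (SAP 2.4.2). For a biologic it is a date that a patient treated per protocol cannot have. The date also has a second possible use: it may open the window in which SCS data are discarded. If it does, valid data collected before the biologic are removed from the primary rank test, and a patient can be left with no value at all.

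The loss would not be random. Protocol 5.5.5 offers biologics as a step-up for patients who stay uncontrolled or have exacerbations, and these are the patients whose SCS use the primary endpoint is meant to capture.

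**Working it through.** **The plan's own figure.** Annualised dose = observed dose × 12 / observed months. The SAP 2.5.2 example gives 280 × 12/7 = 480 mg, as stated.

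**The same patient under rule 4a.** Assume that the seven months ended with a biologic, recorded by year only, in the treatment-start year. The imputed start is first dose minus one day. If the biologic continues to last dose, observed months = 0 and the annualised dose is 0 × 12/0, which is undefined. The SAP has no rule for this case.

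**A dated example (dates assumed).** First dose is 10 March 2019. The biologic truly begins on 20 October 2019, with day and month missing. Rule 4a gives 9 March 2019. The interval from first dose to true start is 224 days, or 224/30.4375 = 7.4 months by the SAP 2.1.1 month length, and all of it is discarded. If the month had been known (October), rule 4c would give 1 October.

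**How far the rules reach.** I applied rules 1 to 4 to every first-dose date in a 365-day year and every true biologic start from Day 1 to Day 364. All dates are taken as equally likely, which is an assumption. Shares are of records with the given missing pattern. Days lost are valid pre-biologic on-treatment days.

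| Missing | Rule | Share | Imputed start | Days lost: maximum (mean) |
|---|---|---|---|---|
| Day | 4a | 4.3% | Day -1 | 30 (9.8) |
| Day | 4c | 46.0% | First of true month | 30 (14.8) |
| Day | 3b | 49.7% | First of true month | 30 (14.3) |
| Day and month | 4a | 50.3% | Day -1 | 363 (121.3) |
| Day and month | 3a | 49.7% | 1 January of next year | 362 (120.7) |
| Whole date | 1 | 100% | Day -1 | 363 (181.5) |

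The last row applies only if rule 1 overrides the lead-in sentence. Rule 3a also discards pre-biologic time, but it keeps everything from first dose to 31 December, so something remains to annualise. In the equal-month branch of 4a, data after the true start would be set to missing anyway. The avoidable loss there is only the days between first dose and true start, though those few days may be the whole evaluable record.

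**The biologic endpoint.** SAP 2.7.1.5 counts patients with a prescription: "Events which occur during on-treatment period will be included". A Day -1 start lies outside the on-treatment period of SAP 2.1.1. The event is lost only if it is dated by treatment start; the prescription date is a separate field.

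**The case against.** The strongest objection is that SAP 2.5.2 never cites 5.1.3.2. The use the SAP states for medication dates is the prior/concomitant classification, and Protocol 6.4.5 sets out its own data collection for biologics. That stands: the link to the primary endpoint is an inference. It rests on step-up therapy being recorded as concomitant medication and on the SAP giving no other rule for an incomplete biologic start date.

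The trigger is also unlikely. Biologics are prescribed by the investigator during the study, concomitant medication is reviewed at every visit and call (Table 6-1), missing values are queried (Protocol 8.3), and primary-variable data are fully source-verified (Protocol 8.1). Because the study stopped early, most patients lack sufficient follow-up (SAP section 4), so long pre-biologic records will be fewer. This limits the size of the problem but does not make the rule correct.

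A reader might infer that every incomplete biologic date is sent to Day -1, or that the whole record is always lost. The documents support neither. Rules 3a, 3b and 4c give dates after first dose, and a biologic with a recorded stop before last dose leaves later data. A reader might also infer that patients drop out of 2.7.1.5. That endpoint is worded by prescription, so the natural date is unaffected, and it is now only descriptive.

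Finally, the zero-month gap does not depend on imputation: a biologic begun on Day 1 with a complete date produces it too. That is correct, and is a reason to close the gap whatever is done about dates.

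**Conclusion.** The point holds as a narrow defect in a derivation rule. Rule 4a, followed as written, can give a biologic a start date that the protocol excludes; rule 1 does the same if it prevails over the sentence that contradicts it. The loss of the whole on-treatment SCS record depends on two conditions: 5.1.3.2 defines the biologic window in 2.5.2, and the biologic continues to last dose. The large losses, up to 363 days, need a missing month or year; the branch with a known first-dose month costs at most 30 extra days.

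The documents give no count of biologic users or of incomplete dates, so an effect on power or bias cannot be computed, and a claim that the primary result is materially distorted would go beyond them. The number of records is probably small. The point is minor, but the repair costs little and protects primary-endpoint data in patients with poor control.

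**What to change.** Add to SAP 5.1.3.2 that an incomplete biologic start date is never imputed before Day 1, and is set to the latest of Day 1, the recorded prescription date (Protocol 6.4.5) and the first day of any known month or year. Provided that prescription precedes first use, each of these is no later than the true start, so the rule keeps no data collected on a biologic.

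In addition:

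- State that this date drives the blanking in 2.5.2 and that the prescription date drives 2.7.1.5.
- Resolve the conflict between the lead-in sentence and rule 1. The adverse-event rules in SAP 5.1.2.2 are a consistent model: a missing year gives no imputed date.
- State how a patient with no evaluable pre-biologic month enters the rank test.

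The Day 1 floor alone recovers nothing. If the prescription date is also missing, a year-only start in the first-dose year becomes Day 1 and the record is still empty. Incomplete prescription dates therefore need to be queried, and the zero-month rule covers what remains.

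The cost is a few sentences and one derivation branch, using dates the protocol already requires. The prescription date may precede first use, particularly where access is slow, so some valid SCS data may still be blanked.

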5.2 Conversion of OCS to prednisolon equivalent

Prednisone 5 mg is comparable to

Drug	Dose	Conversion factor
Deflazacort	6 mg	0.83
Triamcinolone	4 mg	1.25
Dexamethasone	0.75 mg	6.67
Methylprednisolone	4 mg	1.25
Prednisolone	5 mg	1
Betamethasone	0.75 mg	6.67
Prednisone	5 mg	1
Hydrocortisone	20 mg	0.25
Fluocortolone	5 mg	1
Meprednisone	4 mg	1.25

5.3 AEs coding/grading

The MedDRA version which will be available at the time of database lock, will be used for the coding purpose of the adverse events. For coding purpose of the concomitant medications, the available WHO-DD (World Health Organization- Drug Dictionary) version at the time of database lock, will be used.

5.4 Laboratory parameters derivations

The following table shows the criteria for clinically notable laboratory values. Not all parameters have notable criteria defined.

Table 6.3.1 Direction of interest for worst case value for laboratory parameters

Laboratory Parameter	Direction of interest for worst case value
A. Hematology	
Basophils	High
Eosinophils	High
Hematocrit	Low
Hemoglobin	Low
Lymphocytes	Low and high
Monocytes	High
Neutrophils	Low and high
Platelets	Low and high
RBC	Low
WBC total	Low and high
B. Chemistry	
Albumin	Low
Sodium	Low and High
Alkaline Phosphatase	High
ALT/SGPT	High
AST/SGOT	High
Bilirubin Total	High
Blood Urea Nitrogen (BUN)	High
CPK	High
Creatinine	High
Gamma GT	High
Glucose	Low and high
Potassium	Low and high
Uric acid	High

Table 6.3.2 Clinical notable criteria for selected laboratory tests

Laboratory parameter (unit)	Bound for notably low values	Bound for notably high values
Hematology		
Hematocrit (v/v)		
Male 12-17	0.34	
Male 18-65	0.37	
Male >=66	0.34	
Female 12-65	0.32	
Female >=66	0.31	

Laboratory parameter (unit)	Bound for notably low values	Bound for notably high values
Hemoglobin (g/L)		
Male 12-17	100	
Male >=18	110	
Female	95	
Thrombocytes (x10E ⁹ /L)	75	700
WBC's (x10 ⁹ /L)	2.8	16.0
Chemistry		
Alkaline Phosphatase (IU/L)	-	3xULN
Total Bilirubin (µmol/L)	-	34.2
Creatinine (µmol/L)		176.8
Potassium (mmol/L)	3	6
Glucose (mmol/L)	2.78	9.99
ALT/SGPT (U/L)	-	3 x ULN
AST/SGOT (U/L)	-	3 x ULN
BUN/ Urea (mmol/L)		9.99
Sodium (mmol/L)	125	160
Gamma GT (U/L)		3 x ULN
CPK (IU/L)		4 x ULN
Urinalysis		
Dipstick blood		≥ 2+
Dipstick glucose		≥ 2+
Dipstick leukocytes		≥ 2+
Dipstick protein		≥ 2+

v = volume, ULN = upper limit of normal

5.5 Statistical models

5.5.1 Primary analysis

A Van Elteren test will be used to analyze the ranked data with stratifications. The SAS procedure PROC FREQ will be used for this analysis. The test can be done by defining a stratified, three-way table and using the CMH and SCORES=MODRIDIT options. In the TABLE statement, the variable(s) defining the strata appear first, followed by the treatment variable and finally the response variable.

5.6 Rule of exclusion criteria of analysis sets

The following protocol deviations will lead to exclusion of patients from the RAN, FAS, SCR or safety set:

PD Identifier	'PD Description' for Reporting	CP_Exclude from analysis set
INCL01A	Did not sign informed consent	Exclude from all analysis sets

INCL01B	Written Informed Consent obtained after date of a study assessment	All concerned assessments excluded from SCR
TRT01	Received study drug but not randomized	Exclude from RAN, FAS and SAF (also evaluate on case by case basis)
TRT02	Randomized but no study drug given	Patient did not receive a study drug then exclude from FAS and SAF; otherwise do not exclude from any population set
TRT04	Double blind study drug taken prior to baseline FEV1 assessment	Do not consider FEV1 baseline value for analysis
WITH01	Patient not withdrawn from the study even after Withdrawal of informed consent.	Include data up to withdrawal of consent in all analysis sets
WITH07	Blind broken and study drug not stopped	Data before unblinding can be used for efficacy ; otherwise use all data for safety

6 Reference

Zhao YD (2006) Sample size estimation for the van Elteren test—a stratified Wilcoxon–Mann–Whitney test. *Statistics in Medicine*; 25:2675–2687

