9.1 Analysis sets

The screened set (SCR) will include all patients who provided informed consent.

The randomized set (RAN) will include all patients that were randomized. Data from these patients will be analyzed according to the treatment to which the patient was assigned at randomization.

The full analysis set (FAS) will include all randomized patients who received at least one dose of study drug. It was considered reasonable to limit the FAS to patients who took trial medication, because the decision on whether or not treatment is started will not be influenced by the treatment group assignment due to the effective treatment blinding procedures described in [Section 5.4](#). Following the intent-to-treat principle, patients will be analyzed according to the treatment they were assigned to at randomization.

The safety set (SAF) will include all patients who received at least one dose of study drug. Patients will be analyzed according to the treatment they received.

The analysis of the primary objective will be performed on the FAS. The FAS will be used for the analysis of all other efficacy variables. The SAF will be used in the analysis of all safety variables.

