2.1.1 General definitions

Study drug

For this double blind trial, study treatment refers to QAW039 150 mg, QAW039 450 mg or placebo as assigned to a patient at randomization.

Date of first administration study treatment

The date of first administration of study treatment is derived as the first date when a nonzero dose of study treatment was administered as per the Dosage Administration CRF. The date of first administration of study treatment will also be referred as *start of study treatment*.

Date of last administration of study treatment

The date of last administration of study treatment is defined as the last date when a nonzero dose of study treatment was administered as per Dose Administration (e)CRF.

Study day

The study day, describes the day of the event or assessment date, relative to the reference start date. The date of first dose of study medication is defined as Day 1 and the day before the first dose of study medication is defined as Day -1.

The study day is calculated as:

- The date of the event (visit date, onset date of an event, assessment date etc.) – reference start date + 1 if event is on or after the reference start date;
- The date of the event (visit date, onset date of an event, assessment date etc.) – reference start date if event precedes the reference start date.

The reference start date for safety assessments (e.g. adverse events, laboratory abnormality occurrence, vital sign measurements, dose interruption etc.) is the start of study treatment. The reference start date for all other, non-safety assessments (i.e., SCS use, eDiary, patient reported outcomes (PRO) (AQLQ and ACQ) and biologic therapy administered during the treatment period) is the date of randomization.

The study day will be displayed in the data listings. If an event starts before the reference start date, the study day displayed on the listing will be negative.

Time unit

A year length is defined as 365.25 days. A month length is 30.4375 days (365.25/12). If duration is reported in months, duration in days will be divided by 30.4375. If duration is reported in years, duration in days will be divided by 365.25.

Baseline

For efficacy evaluations, the last non-missing assessment, including unscheduled assessments on or before the date of randomization is taken as “baseline” value or “baseline” assessment. In the context of baseline definition, the efficacy evaluations also include eDiary, PRO, biologic therapy.

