2.2 Analysis sets

The screened set (SCR) will include all patients who provided informed consent.

The randomized set (RAN) will include all patients that were randomized. Data from these patients will be analyzed according to the treatment to which the patient was assigned at randomization.

The full analysis set (FAS) will include all randomized patients who received at least one dose of study treatment. It was considered reasonable to limit the FAS to patients who took study treatment, because the decision on whether or not treatment is started will not be influenced by the treatment group assignment due to the effective treatment blinding procedures described in protocol Section 5.4. Following the intent-to-treat principle, patients will be analyzed according to the treatment they were assigned to at randomization.

The safety set (SAF) will include all patients who received at least one dose of study treatment. Patients will be analyzed according to the treatment they received.

The analysis of the primary objective will be performed on the FAS. The FAS will be used for the analysis of all other efficacy variables. The SAF will be used in the analysis of all safety variables.

If an incorrect randomization stratum is inadvertently selected for a patient by the investigator in the IRT, patients will still be included in all analyses. The corrected stratum information as per the CRF data will be used in any analysis models.

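### By default, SAP 5.6 removes patients dosed without randomisation from the Safety Set, which conflicts with the exposure-based definition in protocol 9.1 and SAP 2.2 and is not declared in SAP section 4

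*SAP*

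**What the plan says.** The two documents define the Safety Set almost identically. Protocol 9.1: "The safety set (SAF) will include all patients who received at least one dose of study drug". SAP 2.2: "The safety set (SAF) will include all patients who received at least one dose of study treatment". Both then analyse these patients by the treatment they received. In the same sections the Full Analysis Set carries an extra condition; in the SAP it "will include all randomized patients who received at least one dose of study treatment".

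SAP 5.6 opens its table with "The following protocol deviations will lead to exclusion of patients from the RAN, FAS, SCR or safety set". The description for TRT01 is "Received study drug but not randomized", and the action is "Exclude from RAN, FAS and SAF (also evaluate on case by case basis". No criteria, decision-maker or timing are given for that evaluation.

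SAP 2.2 also states: "The SAF will be used in the analysis of all safety variables". SAP 2.8 puts the safety summaries on the same set, and SAP 2.4.1 does so for exposure. SAP section 4, which lists changes to the protocol's analyses, mentions only that the secondary endpoints become descriptive after early termination.

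**The concern.** A safety population defined by exposure exists so that anyone who took the drug is counted, however they came to take it. The TRT01 row takes out a patient because of how the dose came about. Two rules in the plan then give opposite answers for the same patient, and a programmer cannot follow both.

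At stake are the adverse events, SAEs, laboratory values and exposure time of any such patient in the summary tables. The number of patients is likely to be tiny, but a single serious event can change the reading of a rare category. Membership of the safety population should also follow a rule fixed in advance, and the case-by-case clause leaves it to a judgement that the plan does not describe.

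**Working it through.** The plan has no figure to reproduce here, so the check is a comparison of rules.

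**Step 1: apply each rule to one patient who took at least one dose and was never randomised.**

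| Rule | Condition | In the SAF? |
|---|---|---|
| Protocol 9.1 | at least one dose of study drug | Yes |
| SAP 2.2 | at least one dose of study treatment | Yes on its face (see the objection on SAP 2.1.1) |
| SAP 5.6, TRT01 | dosed, not randomised | No by default, with an open case-by-case evaluation |

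**Step 2: is randomisation an implied condition of the SAF?** Protocol 9.1 and SAP 2.2 both write it into the FAS definition and both leave it out of the SAF definition. The natural reading is that the omission is deliberate.

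**Step 3: does the rest of the SAP 5.6 table follow exposure?** Mostly yes. TRT02 takes a randomised patient out of the SAF only when no drug was given. WITH07 limits efficacy data after a broken blind but keeps all data for safety. Apart from missing consent (INCL01A), TRT01 is the only row that removes a dosed patient from the SAF.

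**Step 4: which outputs lose the patient?**
- Adverse event, SAE and laboratory summaries (SAP 2.8, on the SAF): lost.
- Exposure (SAP 2.4.1, on the SAF): lost.
- Table of protocol deviations (SAP 2.3.2) and table of exclusion reasons (SAP 2.3.3): both are produced on the RAN, which cannot contain an unrandomised patient, so the case does not show there.
- Listings: kept. SAP 2.8 lists all safety data, SAP 2.8.1 lists adverse events from consent onward, and SAP 2.3.3 lists exclusions with reasons for all patients.
- Deaths: SAP 2.8.2 adds a table of all deaths after first dose and names no analysis set. Because SAP 2.8 places safety summaries on the SAF, it is unclear whether a TRT01 death would appear.

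**Step 5: size.** The documents give no TRT01 count. Under protocol 5.3 and 5.5.2, medication numbers come from the IRT, and the first ones are issued at randomisation, so dosing without randomisation should be very rare. Assume for illustration one to three such patients, all in one arm of the planned size, 669/3 = 223. They would make up 1/224 = 0.4% to 3/226 = 1.3% of that arm's safety denominator. Rates of common events would hardly move. A category with no other event would go from 0 to 1 or more.

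**The case against.** The best defence is in SAP 2.1.1: "study treatment refers to QAW039 150 mg, QAW039 450 mg or placebo as assigned to a patient at randomization". If study treatment exists only by randomised assignment, an unrandomised patient never received it, and the TRT01 row merely applies the SAP's own definition. This has some force for the SAP read alone, so a flat claim that the SAP contradicts itself goes a little too far. It does not settle the matter. The protocol's SAF refers to study drug, and the TRT01 row itself says study drug was received. Tying the term to assignment also fits poorly with analysis by treatment received. At the least, the SAP departs from the protocol without saying so.

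A reader might infer that these patients vanish from the report or from every safety table. The documents do not support that: exclusion is a default with a case-by-case opening, the data and the exclusions are listed, and deaths after first dose may be tabulated. Protocol 7.2.2 also requires every SAE after consent to be reported to the sponsor's safety group whatever the analysis set. The loss is confined to summary counts.

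A reader might also infer that the case-by-case decision would be steered by treatment or outcome. Protocol 8.3 settles deviations before database lock and unblinding, which limits selection by treatment. The patient's events would already be in the database, but nothing in the documents shows that they would influence the decision.

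Finally, treatment received may not be well defined. SAP 2.4.1 describes two bottles per patient, and someone dosed outside randomisation might take only one, or a pair that matches no arm. This objection stands, and the fix has to provide for it.

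**Conclusion.** The concern holds as an inconsistency between the TRT01 action in SAP 5.6 and the exposure-based SAF of protocol 9.1 and SAP 2.2, undeclared in SAP section 4. Its consequence is that a dosed, unrandomised patient is left out by default of the SAF-based adverse event, SAE, laboratory and exposure summaries.

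The practical effect is probably very small or nil. That rests on the assumption that IRT dispensing works as described, since no count is available. Efficacy is unaffected, because such patients belong in neither RAN nor FAS under any reading. The correction is still worth making: the rule as written departs from the protocol's definition, and aligning it is cheap.

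**What to change.** Change the TRT01 action in SAP 5.6 to: exclude from RAN and FAS; retain in SAF under the treatment actually received according to the dispensed medication numbers; if the bottles taken match no single arm, show the patient separately in the safety summaries. Let this rule replace the case-by-case clause, so that the awkward cases are covered without an open judgement.

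If the sponsor does intend to keep unrandomised patients out of the SAF, the alternative is to amend the SAF definition, declare the change in SAP section 4, and state where these patients' safety data will be shown.

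The cost of the main fix is one table cell. It has a small downside: a few unrandomised patients may appear in, or beside, the by-arm safety tables, where comparisons otherwise rest on randomisation. A footnote giving their number and arm deals with that.
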